5. CCI [REDACTED]
6. Ophthalmic Examinations:
 - A. Best-Corrected Distance Visual Acuity (BCDVA) by ETDRS.
 - B. External Ocular Examination.
 - C. Assess NIKBUT (at selected centers).
 - D. Schirmer-I test without anesthesia.
 - E. Slit Lamp Examination (SLE) of the anterior segment of the eye (cornea, conjunctiva, anterior chamber, iris, lids and lashes).
 - F. Assess bulbar redness (VBR 10 scale).
 - G. Instill fluorescein and wait 30 seconds.
 - H. Assess fTBUT.
 - I. After 2-5 minutes from the time of fluorescein instillation, assess total corneal fluorescein staining score (NEI, score range 0-15).
 - J. Apply lissamine green.
 - K. Assess total conjunctival lissamine green staining score ([NEI, score range 0-18).
 - L. Perform CCI [REDACTED] eyedrop CCI [REDACTED] (only in patients with CCI [REDACTED])
7. Collect used and unused Study Product (to be checked by independent personnel)
8. Retrieve Patient's Diary for the treatment period.
9. Dispense preservative free artificial tears (AT) eye drops to be administered 3 times daily.
10. Deliver instruction to Patient.
11. Dispense Patient Diary to record adherence to preservative free AT eye drops during the FU period, any new or changes in concomitant medications, any unusual medical conditions.

Visit 5 - Week 8 (day 56±2) FOLLOW-UP & END OF STUDY VISIT or EARLY EXIT VISIT*

1. Concomitant Ocular and Systemic Medications Update.
2. AEs monitoring (recording evaluation, as applicable).
3. Check the Patient's Diary of the Follow-Up period.
4. SANDE questionnaire.
5. CCI
6. Ophthalmic Examinations:
 - A. Best-Corrected Distance Visual Acuity (BCDVA) by ETDRS.
 - B. External Ocular Examination.
 - C. Assess NIKBUT (at selected centers).
 - D. Schirmer-I test without anesthesia.
 - E. Slit Lamp Examination (SLE) of the anterior segment of the eye (cornea, conjunctiva, anterior chamber, iris, lids and lashes).
 - F. Assess bulbar redness (VBR 10 scale).
 - G. Instill fluorescein and wait 30 seconds.
 - H. Assess FTBUT.
 - I. After 2-5 minutes from the time of fluorescein instillation, assess total corneal fluorescein staining score (NEI scale, score range 0-15).
 - J. Apply lissamine green.
 - K. Assess total conjunctival lissamine green staining score (NEI scale, score range 0-18).
 - L. Perform specular microscopy to assess corneal endothelial cells density (at selected sites that have a specular microscope already available).
 - M. Instill tropicamide eye drop solution 1%.
 - N. After 15 minutes/once pupils are adequately dilated perform fundus examination in both eyes.
7. Retrieve the Patient's Diary for the Follow-Up period.

End of Trial (EoT)/End of Study (EOS): as per article 2 (26) of the European Clinical Trial Regulation (CTR), EoT/End of Study (EOS) is the last visit of the last patient globally.

At the investigator's discretion, any patient could be seen for an Unscheduled Visit for safety evaluation.

Premature Discontinuation and Early Exit Visit: (*) In case of premature discontinuation of the study, the patient will be required to perform the Early Exit Visit that will have the same assessments of Visit 4 (in case of early treatment discontinuation before Visit 4) or the same assessments of Visit 5 (in case the discontinuation from the study will occur after the ending of the treatment but before the expected Visit 5). A flag will be inserted in the eCRF to define if the Visit 4 or Visit 5 is a per protocol visit or if it is done as Early Exit Visit.

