1.2 SCHEDULE OF ACTIVITIES

Table 1: Schedule of activities planned during the different visits

	Run-In period		Treatment period		FU period
	V1 Screening (Day -12)	V2 Baseline (Day 1)	V3 Week 2 (Day 13)	V4 Week 4 (EOT) (Days 28)*	V5 Week 8 (EOS) (Days 56)*
Interval Tolerance (days)	±2		±1	±1	±2
Site Visit	X	X	X	X	X
ELIGIBILITY					
Informed consent	X				
Inclusion / Exclusion criteria	X	X			
Demographics, Medical History, Medications	X				
TRIAL INTERVENTIONS					
Randomization		X			
Trial Study Product dispensation**	X	X	X		
Artificial tears dispensation				X	
Patient Instruction	X	X		X	
Application of eye drops by the investigator	X				
Patient's Diary dispensation	X	X		X	
Documentation in patient's medical record of first dose administration by Investigator	X				
Medication dosing compliance verification (diaries)		X	X	X	X
TRIAL PROCEDURES					
Check the Patient Diary		X	X	X	X
SANDE questionnaire	X	X		X	X
CCI		X		X	X

	Run-In period		Treatment period		FU period
	V1 Screening (Day -12)	V2 Baseline (Day 1)	V3 Week 2 (Day 13)	V4 Week 4 (EOT) (Days 28)*	V5 Week 8 (EOS) (Days 56)*
Interval Tolerance (days)	±2		±1	±1	±2
Site Visit	X	X	X	X	X
BCDVA by ETDRS	X	X		X	X
External Ocular Examination	X	X		X	X
NIKBUT (in selected centers)		X		X	X
Schirmer-I test without anesthesia	X	X		X	X
Slit Lamp Examination	X	X		X	X
Redness score (VBR 10)	X	X		X	X
Instill fluorescein	X	X		X	X
fTBUT	X	X		X	X
Corneal fluorescein staining NEI scale	X	X		X	X
Apply lissamine green	X	X		X	X
Conjunctival lissamine green Staining NEI scale.	X	X		X	X
CCI CCI CCI and after CCI eyedrop) ***		X		X	
Specular microscopy (Corneal endothelial cell density) (in selected centers)		X			X
Instill tropicamide eye drops		X			X
Dilated fundus examination		X			X
Collect used/unused Study Product (to be checked by independent personnel)		X	X	X	
Retrieve Patient Diary		X		X	X
Concomitant medications****		X	X	X	X

	Run-In period		Treatment period		FU period
	V1 Screening (Day -12)	V2 Baseline (Day 1)	V3 Week 2 (Day 13)	V4 Week 4 (EOT) (Days 28)*	V5 Week 8 (EOS) (Days 56)*
Interval Tolerance (days)	±2		±1	±1	±2
Site Visit	X	X	X	X	X
Adverse events evaluation		X	X	X	X
LABORATORY TESTS					
Pregnancy Test	X	X		X	

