
 To evaluate the efficacy of the new formulation of rhNGF ophthalmic solution in improving best corrected visual acuity in DED as compared to vehicle 	
 Mean change from baseline in BCDVA score [Time Frame: at weeks 4 (V4) and 8 (V5)]
Safety Objectives	Safety Endpoints

 To evaluate safety/tolerability of the new formulation of rhNGF ophthalmic solution 	
 Safety will be monitored by the incidence and frequency of treatment-emergent adverse events (TEAEs) assessed throughout the study including run-in period.

 To evaluate safety of the new formulation of rhNGF ophthalmic solution 	
 Mean change from baseline in corneal endothelial cell density in both eyes [Time Frame: at week 8 (V5)] Change from baseline in the proportion of patients with vitritis, retinal or vitreal hemorrhages, increase in cup-to-disc ratio, retinal or posterior vitreal detachment, retinal tears, or maculopathy on dilated fundus exam (DFE) in both eyes [Time Frame: at week 8 (V5)] Mean change from baseline in bulbar conjunctival redness (VBR 10 score) in both eyes [Time Frame: at weeks 4 (V4) and 8 (V5)]

 To evaluate tolerability of the new formulation of rhNGF ophthalmic solution. 	
 Treatment discontinuation rate due to tolerability will also be evaluated.
Additional Objective	Additional Endpoint

 Validate an Italian version of the CCI [redacted] 	
 CCI [redacted] CCI [redacted] [Time Frame: Baseline, weeks 4 (V4)]

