- Patients will be evaluated at Screening visit (day -12 ± 2 , V1) after which they will enter a Run-In period with the Study Product vehicle (from day -12 ± 2 to day 1). Evaluations will continue at Baseline visit (day 1, V2), week 2 (day 13 ± 1 , V3), week 4 (day 28 ± 1 , EOT (V4)), and at week 8 (day 56 ± 2 follow-up and EOS (V5)). At the investigator's discretion, any patient could be seen for an Unscheduled Visit for safety evaluation. An Early Exit Visit could be done in case of premature study discontinuation. In case of treatment discontinuation, patients will be asked to complete the assessments at the planned visits as per Protocol. In case of premature discontinuation of the study, the subject will be required to participate at the Early Exit Visit that will have the same assessments of Visit 4 (in case of early treatment and study discontinuation before Visit 4) or the same assessments of Visit 5 (in case the discontinuation from the study will occur after the ending of the treatment but before the expected Visit 5). A flag will be inserted in the eCRF to define if the Visit 4 or 5 is a per protocol visit or if it is done as Early Exit Visit.
- The trial design follows the principles of Quality by Design (QbD) with respect to eligibility criteria, randomization, masking, data quantity, endpoints, data integrity, IMP handling and administration, site feasibility, safety reporting, data monitoring and delegation of responsibilities. Detailed evaluations and timing are presented in § 1.2, 1.3 and 8.

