7.4 TRIAL STOPPING RULES

The Sponsor has the right to discontinue the study at any time for reasonable medical and/or administrative reasons. Reasons for discontinuation have to be documented appropriately. In

this event, no further patients will receive doses of the IMPs, and patients already having received a dose of IMP will not receive any further doses of the IMP but will undergo all safety assessments scheduled after the last dose of IMP, up to and including the end of study examination.

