4.4. Analysis Window/Visit

For safety and efficacy endpoints, data will be evaluated and reported according to the nominal visit at which they have been collected, even if performed out of the tolerance interval limits declared in [Figure 1](#).

Efficacy analyses. Before applying any imputation methods, or any other strategy required by the handling of intercurrent events as detailed in [Section 3.3](#), a remapping will be done for any missing assessment at each planned visit. Remapping is allowed only for missing total scores (i.e. missing data for each item will not be replaced). In case data are missing at a given nominal visit, data collected at any other unscheduled visit (or ETV if done within an acceptable time-window of a previous visit) will be remapped to that visit, if the date of collection is within the tolerance interval limits defined in table of activities in [Section 13.1](#) (i.e. ± 1 for V3 – Day 13, ± 1 for V4 – Day 28, ± 2 for V5 – Day 56). Data collected under a nominal visit at out of tolerance interval limits will be used in the analysis unless the patient is declared an early study withdrawal: in this latter case, the evaluations recorded under the nominal visit will be set to missing and the actual values will be moved to a new timepoint named “Early Termination Visit”. This new timepoint will be only listed.

Safety analyses. Data collected under a nominal visit at out of tolerance interval limits will be treated as described for the efficacy. Data collected at an “Early Termination Visit” will be tabulated, separately from nominal visit values (i.e. Week 4 and Week 8).

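### Patients who leave the study altogether before Visit 4 have no scheduled post-dose fundus exam or specular microscopy, so two named safety endpoints have a small avoidable gap

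*Protocol*

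**What the plan says.** Protocol 3.1, Table 3, names two Week 8 safety endpoints that depend on these exams. One is the mean change in corneal endothelial cell density. The other is described as "Change from baseline in the proportion of patients with vitritis, retinal or vitreal hemorrhages, increase in cup-to-disc ratio" and further posterior-segment findings.

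In Table 1 (Protocol 1.2) the row "Dilated fundus examination" is marked at V2 and V5 only. Specular microscopy is marked at the same two visits, at selected centers. The Visit 4 list in Protocol 8.2 ends with the dye-staining scores and one eye-drop response test, and includes no microscopy, dilation or fundus exam.

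For premature study exit, Protocol 8.2 has two branches. The first assigns "the Early Exit Visit that will have the same assessments of Visit 4 (in case of early treatment discontinuation before Visit 4"). The second assigns the Visit 5 assessments "in case the discontinuation from the study will occur after the ending of the treatment but before the expected Visit 5". The Table 1 footnote and SAP 13.1 repeat these branches. Protocol 4.1 words the first trigger differently: "in case of early treatment and study discontinuation before Visit 4".

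SAP 4.4 says of safety data: "Data collected at an “Early Termination Visit” will be tabulated, separately from nominal visit values".

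**The concern.** The protocol accepts that someone who leaves during follow-up should have both exams before going, but does not provide them for someone who leaves during dosing, and gives no reason for the difference. The second patient has received the product and has a baseline fundus record, yet the plan schedules no later look.

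At stake is the completeness of two safety endpoints in the first study of a new formulation with a new excipient, run without a data monitoring committee. An asymptomatic retinal or endothelial change will not appear in adverse-event reports if nobody examines for it. The early-termination safety table in SAP 4.4 would hold these exams for post-treatment leavers but, as scheduled, nothing from patients who left while on drug.

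**Working it through.** **Step 1. Visit lists side by side** (Protocol Table 1 and 8.2):

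| Visit | Fundus exam | Specular microscopy (equipped sites) |
|---|---|---|
| V1 screening | no | no |
| V2 baseline | yes | yes |
| V4 | no | no |
| V5 | yes | yes |
| Early exit before V4 (V4 list) | no | no |
| Early exit after treatment (V5 list) | yes | yes |

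**Step 2. Does another provision secure the exams?**
- The final visit on withdrawal (Protocol 7.1.2) re-checks what was tested at screening, and neither exam is done at screening.
- Unscheduled visits are at the investigator's discretion and have no prescribed content.
- SAP 4 leaves missing values out of percentage denominators and shows them in a separate row, so unexamined patients drop out of the fundus proportions.

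**Step 3. Who is affected?**
- Under Protocol 7.1.1, patients who stop drug for adverse events, worsening or protocol violations are asked to complete the planned assessments, including V5. Section 6.6.3 says the same when ocular health deteriorates. They are not lost by design.
- Those lost are full study exits before V4: withdrawn consent, loss to follow-up, death, pregnancy, a planned operation, or adverse events and other conditions in which study procedures could harm the patient.
- Adverse-event exits are foreseen: Protocol 7.1.1 and 9.6 mention them, SAP 5.1 has a category for them and SAP 9.1.8 a table.

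**Step 4. The trigger wording.** Take a patient who stops drug at week 2, stays on, and leaves the study at week 6. Under Protocol 8.2 this patient meets both branches: treatment stopped before V4, and study exit came after treatment ended but before V5. Under Protocol 4.1 the first branch does not apply, because the study was not left before V4. The text does not settle whether this patient gets the exams.

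**Step 5. Size.** The only related figure is the sample-size allowance (Protocol 10.1), which reproduces:
- 92 / 0.95 = 96.8, rounded up to 97 per arm; 3 × 97 = 291.
- 291 − 276 = 15 patients, about 5 per arm.

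This counts patients not evaluable for the Week 8 primary analysis. It is not a count of exits before V4, and post-treatment leavers within it would have both exams.

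**Step 6. Illustration of possible bias.** The documents give no event rates, so these inputs are assumptions: 97 per arm, k unexamined leavers, a 1% finding rate in examined patients and a rate q in leavers. The full-arm rate is [(97 − k) × 0.01 + k × q] / 97.

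| q | k = 5 | k = 10 |
|---|---|---|
| 1% | 1.0% | 1.0% |
| 5% | 1.2% | 1.4% |
| 10% | 1.5% | 1.9% |
| 20% | 2.0% | 3.0% |

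Example: k = 5, q = 20% gives (0.92 + 1.00) / 97 = 2.0%. The observed rate is 1.0% in every cell. There is no bias if leavers carry the same risk, and it grows only if their risk is higher.

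**The case against.** The strongest reply is that the protocol already retains the patients who matter most. A reader might infer that the endpoints leave out the people likeliest to have an ocular problem. The documents do not support that: stopping drug for an adverse event or worsening does not end participation, several listed reasons for leaving the study are not ocular, and nothing shows a higher retinal or endothelial risk in leavers. The 13-week rabbit study in Protocol 2.3.2 reported no formulation-related ophthalmic findings.

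A reader might also infer a double standard from Protocol 7.4, under which patients stopped by the sponsor "will undergo all safety assessments scheduled after the last dose of IMP, up to and including the end of study examination". That comparison fails. Section 7.4 concerns patients who stop drug, and 7.1.1 asks individual drug-stoppers to continue assessments too. Patients who leave the study are a different group.

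Other safeguards exist. The Visit 4 list includes visual acuity, slit-lamp examination and adverse-event review, and sight-threatening events are reported as serious. Some leavers cannot or will not attend: those who died or were lost cannot, and Protocol 7.1.2 asks only for what is feasible. Sampling uncertainty is also appreciable. With 92 examined in an arm and no finding, the one-sided 95% upper bound is 1 − 0.05^(1/92) = 3.2%.

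Finally, exams at an exit visit would not enter the Week 8 tables, because SAP 4.4 reports early termination separately.

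These points limit the size of the problem and the claim of bias. They do not close the gap in the visit lists: none of the safeguards prescribes a dilated fundus exam or an endothelial count. The last point is a reason to add a reporting rule alongside the exams.

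**Conclusion.** The gap is real and narrow. Dosed patients who leave the study before Visit 4 have no scheduled post-baseline value for two named safety endpoints, while those who leave after treatment do. Informative missingness is plausible because adverse-event exits are foreseen, but it is not demonstrated, and the direction and size of any bias are unknown.

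The number affected cannot be derived from the plan. About 15 of 291 is a rough planning figure and should not be quoted as expected exits before Visit 4, nor should a cluster of events among leavers be assumed. Specular microscopy is limited to selected sites, so the endothelial endpoint is incomplete for a second reason and gains fewer values from a change. The efficacy analyses are unaffected. This is an inexpensive improvement to safety ascertainment, not a flaw that undermines the trial.

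**What to change.** 1. In Protocol 8.2, the Table 1 footnote and the SAP 13.1 footnote, add the dilated fundus exam to the early exit visit before Visit 4, with specular microscopy at equipped sites when a V2 value exists. Align the synopsis, which carries the same rule.
2. Reconcile the trigger in Protocol 8.2, the Table 1 footnote and SAP 13.1 with that in Protocol 4.1, so that a patient who stops drug early and leaves the study later falls under one branch only.
3. In the SAP, tabulate the results at the early-termination time point already planned in section 4.4. Add by arm (a) the number with any post-baseline fundus finding at Week 8 or early termination, (b) the corresponding summary for endothelial density, and (c) the number of dosed patients with no post-baseline exam, with reasons.

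The cost is a short protocol amendment, one eCRF page enabled at the early exit visit and one extra safety table. Both exams were already due at Visit 5 for these patients, so they are moved rather than added. The drawback is a longer exit visit with pupil dilation for a few patients, some of whom may decline. If the protocol can no longer be amended, item 3 can still be done for whatever data exist, and the count of unexamined patients will show how much the gap matters.

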8.3 ASSESSMENTS AND CLINICAL DEFINITIONS

Table 6: List of assessments

Assessment type	Parameters to be analyzed (units)
SANDE questionnaire	
SANDE questionnaire includes two CCI-based questions that assess:
 
 (i) DED symptom frequency (from 0 to 100) (ii) DED symptom severity (from 0 to 100) 
compiled by the patients.
 
The global SANDE score (from 0 to 100) is calculated by multiplying the frequency score by the severity score and obtaining the square root.
 
SANDE is copyrighted by Massachusetts Eye and Ear Infirmary (MEEI). A license will be purchased prior to use in the clinical trial.

CCI	
Scores for sub-scales within the dimensions of CCI (intensity 24h and past 2 weeks: 0-10), CCI (intensity: 0-10, time spent thinking about CCI 0-100%), CCI (interference in activities of daily life: 0-10, time spent thinking about CCI CCI
 
CCI CCI CCI is a validated questionnaire that is copyrighted by the CCI CCI A license will be purchased prior to use in the clinical trial. This form will be administered to all subjects but completed only by those that either have CCI or have filled this form before.

NIKBUT	
Non-Invasive Keratograph tear Break-Up Time (measured in seconds) will be assessed at select centers that have the Oculus keratograph 5M (Oculus, Inc., Arlington, WA) Two types of NIKBUT will be collected:
 
 (i) NIKBUT-first is the time at which the first distortion is recorded, (ii) NIKBUT-average is the average time of first breakup incidents in different cornea locations during recording
Schirmer-I without anesthesia	
After NIKBUT, but prior to slit-lamp examination and vital dye staining, Schirmer-I test will be performed without anesthesia to determine wetting of the strip within 5 minutes and the length of the moistened strip will be measured in millimeters (mm).

Slit lamp examination	
A slit-lamp examination of ocular adnexa (lids, lashes, conjunctival fornix, lacrimal gland and drainage) and anterior segment (cornea, conjunctiva, aqueous humor, iris, lens, vitreous humor) will be performed using white light and prior to vital dye instillation.

VBR 10 scale	
Bulbar conjunctival redness will be assessed at the slit-lamp using white light prior to vital dye instillation and graded according to the Validate Bulbar Redness (VBR 10) scale that has 10 reference images with increasing bulbar redness. The scale starts at grade 10 and has 10-point steps between reference images (score range 10- 100)

Assessment type	Parameters to be analyzed (units)
Fluorescein Tear Break-Up Time (fTBUT)	
fTBUT will be measured by determining the time to tear film break-up. The fTBUT will be performed after instillation of 1 drop of fluorescein solution into the inferior conjunctival cul-de-sac of each eye. To thoroughly mix the fluorescein with the tear film, the subject will be instructed to blink several times. In order to achieve maximum fluorescence, the examiner should wait approximately 30 seconds after instillation before evaluating fTBUT. With the aid of a slit lamp at 10X magnification using cobalt blue illumination, the examiner will monitor the integrity of the tear film, noting the time it takes to form lacunae (clear spaces in the tear film) from the time that the eye is opened after the last blink. The fTBUT will be measured twice during the first minute after the instillation of the fluorescein. If the 2 readings differ by more than 2 seconds then a third reading is taken.
 
The fTBUT value will be the average of the 2 or 3 measurements. The measured value will be expressed in seconds.

Corneal fluorescein staining	
To avoid the phenomenon of quenching, which is increased in dry eye patients, staining will be assessed after 2-5 minutes from fluorescein instillation for fTBUT evaluation. Examination will be performed at the slit-lamp using blue light. Corneal fluorescein staining will be graded according to the NEI scale (5 zones, each zone score 0-3, total score range 0-15).

Lissamine green conjunctival staining	
Lissamine green will be applied to the lower conjunctival fornix and bulbar conjunctival staining will be assessed at the slit-lamp using white light within 2 minutes of lissamine green application. Staining will be scored according to the NEI grading scale (6 zones, each zone score 0-3, total score range 0-18).

CCI CCI CCI (to perform only in patients with CCI CCI)	
1 drop of CCI (CCI will be instilled in the inferior fornix of the palpebral conjunctiva of each eye. After 30 seconds of instillation, CCI will be recorded and will be compared to a pre-test CCI

Specular microscopy	
Corneal endothelial cell density will be determined using specular microscopy and expressed as the number of cells/mm² using the Cell Density readout provided by the software.

Dilated fundus exam	
After specular microscopy, mydriatic drops will be instilled in both eyes and once adequate dilation is achieved, a fundal exam shall be performed to examine the vitreous, retina and optic nerve for vitritis, vitreal or retinal hemorrhage, maculopathy, retinal tears or detachment, posterior vitreous detachment, optic nerve appearance, and optic nerve cup:disc ratio.

